Clinical assessments: Height (screen only), Weight ECOG performance status Blood pressure, pulse	X X X	X X X	X	D1 D1 D1	X X X	X (until PD) X (until PD)
Adverse events		Cumulative recording ⁷⁾ (whenever observed/applicable)				X ⁹⁾
Concomitant treatments	X	X		D1	X	X ¹⁰⁾
Clinical laboratory tests Hematology, Chemistries, and Urinalysis LH, FSH Pregnancy test (β-HCG)	X X X ⁸⁾	X	X ¹¹⁾	D1 ⁴⁾ D1	X X	
Tumor tissue collection	X ¹⁴⁾					
Pharmacokinetics: - Sparse PK sampling ¹⁷⁾ - PK sub-study ¹²⁾		X (X)	(D2-D4)	Cycle X D1 ¹²⁾ (once, if not done at C1)		
Cardiac function test LVEF (ECHO or MUGA) ECG (12-lead)	X ^{2A)} X	X ¹²⁾	D2 ¹²⁾	End of C3, C6, C7, C8 ¹⁶⁾ D1	X X	X ⁹⁾ X ⁹⁾
Tumor imaging/evaluation	X ^{2B)}			End of C3 + C6	X	X
Quality of Life questionnaire	X			End of C3 + C6	X	X
Survival follow-up						X
Patient registration	X					
Eligibility criteria review	X	X ¹⁵⁾				
Randomization ¹³⁾	D-1 to D-4 ¹³⁾					

Study treatment		X		D1		
-----------------	--	----------	--	-----------	--	--

- 1) A window of +/- 3 days will be allowed for scheduled visits/actions, +/- 7 days for 3 monthly follow-ups. If a procedure or visit falls on a public holiday, the patient should be scheduled for the next working day.
- 2) Pre-study evaluations dating back more than 2 weeks prior to treatment start are acceptable.
 - 2A) LVEF: In absence of intercurrent chemotherapy or cardiac medical history, results dating back up to 8 weeks will be acceptable.
 - 2B) Tumor imaging: Assessments of indicator lesions up to 4 weeks prior to treatment start (C1D1) will be considered valid for baseline evaluation.
- 3) Patients who have not recovered sufficiently from treatment-related adverse events within 3 weeks may have their retreatment delayed by up to 2 weeks; patients who cannot be retreated 5 weeks after previous dose, will not receive further study treatment but will still be followed for outcome.
- 4) Start of a new cycle is planned every 3 weeks unless treatment delay is required due to residual toxicity. Per footnote 1, a window of up to 3 days is allowed to schedule tests prior to the anticipated day of retreatment, to assure sufficient recovery from treatment-related adverse events ('toxicity') prior to dosing.
- 5) A full End-of-Therapy assessment will be also required whenever a patient is being withdrawn from the study. The reason(s) for discontinuation will be documented.

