6.1.2 Reconstitution and administration

Reconstitution and dilution: Physiological saline (0.9 % NaCl solution) will be used as solvent for the reconstitution and dilution of AEZS-108 solution.

Four (4) mL of saline will be added per 100 mg vial, resulting in a concentration of 25 mg AEZS-108 per mL of the reconstituted solution.

The appropriate volume of reconstituted AEZS-108 solution will be diluted with physiological saline, such as to contain the desired amount of drug substance in an infusion volume of about 250 mL.

Stability in diluted solution: Not more than 1 hour should elapse between dissolution of the lyophilisate and the preparation of the solution for infusion. The diluted solution for infusion can be stored at room temperature, but must be completely infused within 7 hours after dissolution of the lyophilisate.

Administration (Infusion): The administration schedule is as follows:

Dose:	267 mg/m ² ; For each treatment course, dose calculation will take into account the body surface area (BSA) as derived from the patient's height and current body weight. (Note: If the body weight is +/- 10% of the body weight measured at day 1 of the preceding cycle, the body weight measured at day 1 of the preceding cycle may be used for calculating the dose to be prepared in the pharmacy). Appendix 1 provides a nomogram and reference to online BSA calculators for the determination of the BSA.
Route:	Intravenous infusion over a period of about 2 hours
Frequency:	Every Day 1 of 21-day (3-week) cycles
Duration:	The proposed maximum duration is 9 cycles. An individual patient will be withdrawn from study as soon as disease progression indicates treatment failure or poor tolerability requires withdrawal. (see Section 5.3 for withdrawal criteria).
Premedication	Recommended prophylactic antiemetic: 8 mg dexamethasone (see Section 6.3)

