8.5 Procedures at end of study treatment

A patient who is going off study treatment (see [Section 5.3](#)) – will have the assessments/investigations specified below.

As an end-of-cycle assessment, it should be scheduled 3 to 5 weeks (Day 21 to 35) after the last dose. Additional visits/assessments may be indicated to follow-up unresolved adverse events.

- **Interval history** and symptom-directed examination
- **Clinical laboratory** tests (hematology, chemistries, urinalysis, hormones)
- **Cardiac function:**
 - 12-lead electrocardiogram (ECG)
 - Left ventricular ejection fraction (LVEF): Echocardiogram or MUGA
- **Quality of Life:** questionnaires
- **Tumor imaging (CT or MRI):** evaluation of time-point response by comparison with target and non-target lesions defined at screening (baseline)
- **Final evaluations:** best response, reason for discontinuation, investigator's overall judgment on tolerability of study treatment

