#### 7.2.7.2 Mixed Model Analysis

##### 7.2.7.2.1 Hypothesis

The hypothesis for the HRQL endpoint – change over time in the QLQ-C30 GHS/QOL is as follows:

- H0: There is no difference in health-related quality of life based on the EORTC QLQ C-30 GHS/QOL scale between AEZS-108 and doxorubicin treated subjects.
- Ha: Treatment with AEZS-108 is associated with better health-related quality of life based on the EORTC QLQ C-30 GHS/QOL scale as compared to treatment with doxorubicin.

The same set of hypotheses holds for QLQ-EN24.

HRQL assessments are performed at the following visits:

Screening, end of cycles 3 and 6, end of therapy (3-5 weeks after last dose) and at post therapy follow-up (every 3 months).

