#### 7.2.7.2.3 Description of mixed model with assumptions

Changes over time in QLQ-C30 Global Health Status/QOL scores and in QLQ-EN24 scores will be compared between treatment groups using a restricted maximum likelihood-based mixed model for repeated measures (MMRM) data under the missing at random (MAR) assumption (Mallinckrodt et al, 2008).

The dependent variable of this model will be the change of QLQ-C30 Global Health Status/QOL score or the QLQ-EN24 score measured at the end of cycles 3 and 6, at the end of therapy and at post therapy follow-up as compared to baseline (denoted by HRQL). The model will include the fixed, categorical effects of treatment (trt), visit (visit), and treatment-by-visit interaction (trt\*visit). As there is only a limited amount of time points per subject and given the possibility that not all time points are equally spaced in time, time is entered into the model as the categorical variable visit. The random subject effects

are not explicitly formulated in the model form, but will be modelled as part of the within-subject error correlation structure. For this purpose, an unstructured covariance matrix will be used, allowing for different variances / covariances across subjects. If the analysis using the unstructured covariance matrix fails to converge, the following covariance structures will be tested: heterogeneous Toeplitz, heterogeneous compound symmetry, Toeplitz and compound symmetry. The covariance structure converging to the best fit, as determined by Akaike's information criterion, will be used as the primary analysis. The Kenward-Roger approximation will be used to estimate denominator degrees of freedom. The least square means for each treatment group and the treatment difference will be presented together with the 95% confidence interval and p-value.

The pseudo SAS code of the primary model is as follows:

```
proc mixed data = HRQLdataset method = reml;
  class PatID trt visit;
  model HRQL = trt visit trt*visit baseline baseline*visit / noint ddfm = kr;
  repeated r / subject = PatID type=un;
run;
```

where PatID represents the individual subject id.

The mixed model will provide estimates of the treatment effect and of the treatment difference at each visit until end of treatment, together with their 95% confidence intervals.

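### The QoL mixed model treats end of therapy as one visit although it falls anywhere from about week 3 to week 29, or week 45 with maximum delays, so its arm contrast is not taken at a common time.

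*SAP*

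**What the plan says.** SAP 7.2.7.2.3 specifies a restricted-maximum-likelihood mixed model for repeated measures. The response is change from baseline in the QLQ-C30 global score or the QLQ-EN24 scores, "measured at the end of cycles 3 and 6, at the end of therapy and at post therapy follow-up". On timing, "time is entered into the model as the categorical variable visit"; the reasons given are the small number of time points and their possibly unequal spacing. The model statement is "model HRQL = trt visit trt*visit baseline baseline*visit / noint ddfm = kr", so it has no term for time on study or cycles received. The planned output includes "estimates of the treatment effect and of the treatment difference at each visit until end of treatment", and also least-squares means by arm with a treatment difference and p-value. SAP 7.2.7.2.1 frames the hypothesis as one about change in scores with time.

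The protocol ties the end-of-therapy visit to the individual patient. Section 8.5 says "it should be scheduled 3 to 5 weeks (Day 21 to 35) after the last dose". Flow chart footnote 5 adds: "A full End-of-Therapy assessment will be also required whenever a patient is being withdrawn from the study". The visit can therefore follow any cycle, including the first.

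SAP 4.2 defines time for efficacy summaries from randomisation, but the QoL model does not use that convention. The SAP has no windowing rule for questionnaires and does not declare QoL at stopping therapy as a separate, event-anchored quantity.

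**The concern.** A categorical visit factor deals with unequal gaps when every patient has the same visits at roughly the same times. It does not deal with a single label that falls at week 4 for one patient and week 28 for another. Progression and poor tolerability end treatment, and the trial is designed to find arm differences in outcomes of that kind. If one arm stays on treatment longer, its end-of-therapy questionnaires come later on average. Any general drift in QoL then appears as an arm difference at that visit even when the underlying trajectories are identical. A treatment difference averaged over visits would carry part of the same shift, because end of therapy and the follow-up visits after it are among the levels averaged.

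A second gap is labelling. Under protocol 8.4.5 the cycle 3 and cycle 6 questionnaires are completed alongside the checks for continuing treatment, and section 8.5 describes the end-of-therapy visit as an end-of-cycle assessment. A questionnaire from a patient who stops at one of these evaluations could carry either label, and no rule decides.

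**Working it through.** **Plan's own figure.** The documents give no sample size, power or week range for the QoL model, so there is nothing to reproduce.

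**Inputs from the documents.** Cycles are 3 weeks long and AEZS-108 has a proposed maximum of 9 cycles (protocol 6.1.2). Re-treatment can be delayed by up to 2 weeks (6.1.3, 6.2.3). The end-of-therapy visit comes 3 to 5 weeks after the last dose (8.5).

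**Step 1: when end of therapy falls.** For k cycles received and a dosing interval of L weeks, counted from cycle 1 day 1:

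end-of-therapy week = (k - 1) x L + 3 to (k - 1) x L + 5

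| Cycles received | No delay (L = 3) | Maximum delay every cycle (L = 5) |
|---|---|---|
| 1 | 3-5 | 3-5 |
| 2 | 6-8 | 8-10 |
| 3 | 9-11 | 13-15 |
| 6 | 18-20 | 28-30 |
| 9 | 27-29 | 43-45 |

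For patients stopping after one or two undelayed cycles, the visit comes before the nominal end of cycle 3 (week 9). After three cycles it coincides with it. After seven to nine it comes later than the nominal end of cycle 6 (week 18).

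**Step 2: illustration of the size (all assumptions).** Assume a constant probability c of receiving the next cycle, no delays, and end of therapy 4 weeks after the last dose. Then the mean end-of-therapy week = 4 + 3 x (c + c^2 + ... + c^8), where c^5 is the share reaching cycle 6. That share is varied from 40 % to 65.1 % on AEZS-108. The upper value is the share completing six cycles in the Phase II endometrial study (protocol 1.2.2). For doxorubicin, c is raised to the power h, with h = 1, 1.33 or 1.5 as the ratio of stopping hazards.

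Example with 65.1 %: c = 0.651^(1/5) = 0.918 and the mean is 20.6 weeks. With h = 1.33, c = 0.892 and the mean is 18.8 weeks. The gap is 1.79 weeks. Shift in the contrast = gap x drift.

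| Reaching cycle 6, AEZS-108 | h | Mean week, AEZS-108 | Mean week, doxorubicin | Gap (weeks, unrounded means) | Shift at 0.25 / 0.5 / 1 point per week |
|---|---|---|---|---|---|
| any of the three | 1 | same | same | 0 | 0 / 0 / 0 |
| 65.1 % | 1.33 | 20.6 | 18.8 | 1.79 | 0.45 / 0.89 / 1.79 |
| 65.1 % | 1.5 | 20.6 | 18.0 | 2.59 | 0.65 / 1.29 / 2.59 |
| 50 % | 1.33 | 17.5 | 15.4 | 2.11 | 0.53 / 1.06 / 2.11 |
| 50 % | 1.5 | 17.5 | 14.5 | 3.00 | 0.75 / 1.50 / 3.00 |
| 40 % | 1.33 | 15.5 | 13.3 | 2.17 | 0.54 / 1.08 / 2.17 |
| 40 % | 1.5 | 15.5 | 12.4 | 3.04 | 0.76 / 1.52 / 3.04 |

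The within-arm SD of the end-of-therapy week is about 9 weeks. The sign follows the drift: if scores worsen with time, the arm treated longer looks worse. The calculation takes the drift as linear and unrelated to the reason for stopping.

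**Step 3: the shared label.** Undelayed end of cycle 3 is 21 days after dose 3, which is the first day of the Day 21 to 35 end-of-therapy interval. One visit can satisfy both descriptions. The schedules list them in separate columns, and neither document says how such a form is stored.

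**The case against.** - **The time-based contrasts largely exist.** The model already gives arm differences at the ends of cycles 3 and 6, nominally weeks 9 and 18. These move only with treatment delays. This stands, and it confines the problem to end of therapy, follow-up and any average that includes them.
- **End of therapy does have an anchor.** QoL 3 to 5 weeks after the last dose is an interpretable quantity, so calling the estimate meaningless would go too far. The valid criticism is that the SAP does not declare this quantity and places it in a model whose hypothesis is about change with time.
- **No bias is shown.** At full dose the treatment caps are almost the same: 9 cycles against 550/60 = 9.17 doses. With equal durations both arms average over the same mix of times and the systematic shift vanishes. This stands. A reader might infer a bias of known size or direction, but the documents fix neither the drift nor the gap.
- **Loss of cycle 3 and 6 data is not established.** A reader might infer that these values will be missing for exactly the patients doing worst. The documents give no storage rule, and patients also stop for reasons such as consent or relocation (protocol 5.3). If a form were stored only as end of therapy, its score would stay in the likelihood, which fits the missing-at-random assumption in SAP 7.2.7.2.2. That protection is partial, because the covariance between cycle 3 and end of therapy would be estimated from patients who have both forms.
- **Windows do not remove all spread.** End of therapy after one to two cycles (weeks 3-8) or four to five cycles (weeks 12-17) falls between weeks 9 and 18 or before them, and delays can push a cycle 6 form to weeks 28-30. This stands and shapes the fix.

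**Conclusion.** The point holds as a minor one. End of therapy is a single level of the visit factor, its timing spans weeks 3-5 to 27-29 (43-45 with maximum delays), nothing in the model adjusts for this, and an arm difference at that visit is a planned output. Whether that difference is distorted depends on whether treatment duration differs by arm. The illustrative shift of about 0.4-3 points rests on assumed stopping patterns, assumed gaps of 1.8-3 weeks and an assumed drift of 0.25-1 point per week; with equal durations it is zero. Needless missing values at cycles 3 and 6 are a possibility that depends on an unstated rule, not a finding. QoL lies outside the OS, PFS and ORR hierarchy in SAP 7.4, so no primary or key secondary conclusion changes.

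**What to change.** Amend SAP 7.2.7.2.3 as follows:

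1. Assign every post-baseline questionnaire, including end of therapy and follow-up, by its actual date to contiguous windows of weeks since randomisation. Centre them on weeks 9, 18, 27 and then every 12 weeks (39, 51 and so on).
2. State the limits. Midpoints give boundaries at weeks (9 + 18)/2 = 13.5, (18 + 27)/2 = 22.5 and (27 + 39)/2 = 33. Add an early window for patients stopping after one or two cycles, closing just before the earliest scheduled end-of-cycle-3 date.
3. When two forms fall in one window, use the one closest to the target week, with a stated tie-break.
4. Use the window as visit in the model, and make the week 9 and week 18 arm differences the reported contrasts.
5. Show end of therapy descriptively, labelled as an event-anchored summary.

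This needs SAP wording and a derivation step on dates already collected, and it agrees with SAP 4.2. It also removes the labelling question, because the date decides the window. The costs are sparse late windows, some remaining time spread within windows, and delayed cycle 3 or 6 forms that may move to the next window. It cannot recover QoL after progression: protocol 8.6.1 schedules questionnaires only until progression and 8.6.2 specifies none, so those patients remain missing at later windows.

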### 7.3 Interim Analyses

The Data and Safety Monitoring Board (DSMB) will review data periodically throughout the trial. The DSMB may recommend stopping the trial for safety at any time or for futility at the interim looks. Two planned interim analyses will be conducted, one for futility only and one for both safety and efficacy. The first for a futility analysis only will be conducted at 1/3 of information time (i.e., approximately at 128 death event time). The interim efficacy/safety analysis is planned at 50 % of information time (when approximately 192 death events take place).

In the interim efficacy/safety analysis, OS, the primary efficacy outcome of the study, will be analyzed using a two-sided log-rank test. The Lan-DeMets implementation of the O'Brien Fleming boundary will be employed to control the overall Type I error rate at 0.05. The nominal p-values for the planned second interim and the final analyses will be 0.003051 and 0.049002, respectively.

The interim analysis may not be binding. However, if the interim analysis results demonstrate strong evidence of efficacy, the DSMB may request a meeting with the FDA to discuss potential early termination of the study.

### 7.4 Adjustments for Multiplicity

One non-binding efficacy interim analysis is planned for this study. Lan-DeMets implementation of the O'Brien-Fleming alpha-spending function will be used to control

the overall Type I error rate at 0.05. The study has one primary efficacy endpoint; no p-value adjustment for multiple endpoints is required.

Two key secondary efficacy variables, PFS and ORR will also be analyzed for potential labeling claims. Hierarchical testing procedures will be used to control the Type I Error at the 0.05 level. Specifically, the superiority of the active treatment will be tested at a two-sided significance level of 0.05 for OS first, then for PFS, and then for ORR. The superiority claim for an efficacy outcome can be made only if all previous claims are successfully made.

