9.9 Interim analyses

The Data and Safety Monitoring Board (DSMB) will review data periodically throughout the trial. The DSMB may recommend stopping the trial for safety at any time or for futility at the interim looks. Two planned interim analyses will be conducted, one for futility only and one for both safety and efficacy. The first for a futility analysis only will be conducted at 1/3 of information time (i.e., approximately at 128 death event time). The interim efficacy/safety analysis is planned at 50 % of information time (when approximately 192 death events take place).

In the interim efficacy/safety analysis, OS, the primary efficacy outcome of the study, will be analyzed using a two-sided log-rank test. The Lan-DeMets implementation of the O'Brien Fleming boundary will be employed to control the overall non-binding Type I

error rate at 0.05. The nominal p-values for the planned second interim and the final analyses will be 0.003051 and 0.049002, respectively.

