### **4.3 Tumor Assessment Schedule**

Tumor assessments will occur every 3 cycles ( $\pm 7$  days) during ongoing treatment, then if required beyond the end of treatment every 3 months ( $\pm 7$  days) while the patient is on study. The last assessment will occur when approximately 384 randomized patients have died.

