#### 7.1.1 OS: Definition

OS is defined as the time from randomization to death for any cause during the study. Patients without confirmed vital status are censored on the day they are last known alive. Every reasonable effort will be made to establish vital status of each patient on the last day of the study, that is, the clinical cutoff date established after approximately 384 patients have died. OS will be calculated as follows:

For those who die during the study,

$$\text{overall survival (days)} = \text{date of death} - \text{randomization date} + 1;$$

For those who are alive or vital status cannot be determined at the end of the study,

$$\text{overall survival (days)} = \text{date of censoring} - \text{randomization date} + 1, \text{ with censor indicator indicating a censor.}$$

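### Does the OS–PFS–ORR hierarchy lose its 5% error control because the SAP sets no PFS and ORR rule for an early efficacy stop?

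*SAP*

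**What the plan says.** SAP 7.4 names two key secondary outcomes: "PFS and ORR will also be analyzed for potential labeling claims". It then makes a claim of control, "Hierarchical testing procedures will be used to control the Type I Error at the 0.05 level", and gives the order and level: superiority "will be tested at a two-sided significance level of 0.05 for OS first, then for PFS, and then for ORR". SAP 7.2.5 repeats the two-sided 0.05 level for the PFS log-rank test, and 7.2.2 gives the ORR test.

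The interim rules sit in SAP 7.3 and Protocol 9.9. A futility look is planned at about 128 deaths and an efficacy and safety look at about 192. At the second look, "OS, the primary efficacy outcome of the study, will be analyzed using a two-sided log-rank test". The nominal levels for OS are 0.003051 at that look and 0.049002 at the final analysis. PFS and ORR are not named for any interim test. On stopping, "The DSMB may recommend stopping the trial for safety at any time or for futility at the interim looks". SAP 7.3 adds that with strong interim efficacy "the DSMB may request a meeting with the FDA to discuss potential early termination of the study", and 7.4 calls the look non-binding.

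The closing date appears in several places. SAP 4.3: "The last assessment will occur when approximately 384 randomized patients have died". SAP 7.1.1 identifies the last day of the study as "the clinical cutoff date established after approximately 384 patients have died". SAP 7.2.1 ends ORR assessment at progression or at about 384 deaths. SAP 7.2.4 counts PFS events up to the end of the study.

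**The concern.** A fixed sequence at full alpha is valid when each endpoint is tested once, at a time set in advance. OS is tested at up to two looks. If OS crosses at 192 deaths and the study then ends, the gate to PFS opens early, and the only level the SAP supplies for PFS is 0.05. The OS result would then have chosen the look at which PFS is tested. Death counts as a PFS event, so the two statistics are correlated, and a favourable OS result tends to come with a favourable chance result on PFS. The 5% claim would no longer be guaranteed, and these are the endpoints meant to support labelling claims. The trial is open-label, so a timing rule settled after the OS result is known would also be hard to defend.

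**Working it through.** **1. The plan's own figures.** Lan-DeMets O'Brien-Fleming spending, 0.025 per side, information fraction 192/384 = 0.5:

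- Spent per side at the interim: 2 × [1 − Φ(2.2414/√0.5)] = 2 × [1 − Φ(3.170)] = 0.001525. Doubled, this is 0.003051, so z = 2.9626.
- Final boundary, solved so that the total is 0.025 per side with correlation √0.5 between looks: z = 1.9686, nominal 0.0490.

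Both agree with SAP 7.3. OS itself is controlled.

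**2. How often the early path opens.** Medians of 12 and 9 months (SAP 7.5) give a hazard ratio of 0.75 under exponential survival.

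- Drift at 384 deaths: |ln 0.75| × √(384/4) = 0.2877 × 9.798 = 2.819.
- At 192 deaths: 2.819 × √0.5 = 1.993.
- P(cross) = P(Z > 2.9626 − 1.993) = 0.166. It is 0.078 at hazard ratio 0.80 and 0.312 at 0.70.

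**3. PFS information at that look (assumed).** With 500 patients accrued uniformly over 24 months, exponential survival and no dropout, 192 deaths fall at month 20.3 with about 424 enrolled, and 384 deaths at month 35.6. Assumed equal PFS medians of 3, 5 and 7 months give 334/494 = 0.68, 282/471 = 0.60 and 241/439 = 0.55.

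**4. Error if PFS is tested at 0.05 at whichever look OS crosses.** Let Z1, Z2 be the OS statistics and Y1, Y2 the PFS statistics, with no true PFS effect:

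error = 2 × [P(Z1 > 2.9626, Y1 > 1.96) + P(Z1 ≤ 2.9626, Z2 > 1.9686, Y2 > 1.96)].

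Example, correlation 0.5 and information 0.60: 2 × (0.01472 + 0.01292) = 5.53%.

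**5. Error if PFS is tested once, at the final analysis.** The event is an OS rejection together with Y2 > 1.96. Its probability cannot exceed P(Y2 > 1.96) = 0.025 per side, whatever the correlation or the OS effect.

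| Assumed OS–PFS correlation | Tested where OS crosses, OS HR 0.75 | Highest over OS HR 0.58–0.91 | Tested once at the final, OS HR 0.75 |
|---|---|---|---|
| 0.3 | 4.96–5.07% | 5.34% | 4.73–4.74% |
| 0.5 | 5.40–5.61% | 5.64% | 4.94–4.95% |
| 0.7 | 5.69–6.01% | 6.05% | 5.00% |

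Ranges cover PFS information 0.55 to 0.68. At correlation 0.9 the highest value over the OS effect is about 6.8% at information 0.55 and 6.9% at information 0.5, so 6% is not a ceiling. At correlation 0.3 with a smaller OS effect the error falls below 5%: 4.3–4.4% at hazard ratio 0.80 and about 3.3% at 0.85.

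**6. Which case does the plan describe?** The inflated column needs a PFS test at 192 deaths. SAP 7.3 and Protocol 9.9 name OS alone for that look. SAP 7.1.1 defines the last day of the study by about 384 deaths, and that is the natural reading of the end of study in 7.2.4. SAP 4.3 and 7.2.1 stop tumour assessment at the same point. SAP Appendix E lists one set of PFS and ORR tables and no interim set. All of this describes the last column.

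**The case for a change.** The strongest case for a change is that 7.4 makes a positive claim of control and 7.3 contemplates early termination, so the claim should hold on that path too. Under the sponsor's own assumptions OS crosses at the interim about one time in six, which is not remote. The 384-death anchors were written for a study that runs its course and do not say what happens in one that stops at 192. Silence also does not rule out testing PFS at 0.05 at both looks, which would give up to 8.3% at information 0.5. A sentence would cost nothing at the final analysis.

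Part of this stands. No section gives a PFS or ORR rule for an early efficacy stop, and the arithmetic for an early test at 0.05 is right. What does not stand is that the plan leads there. For the inflation to arise, OS must cross, the DSMB must choose to seek the FDA meeting, the study must actually end despite a non-binding look, and the sponsor must then test PFS at a full 0.05 on data no section designates for that purpose. Efficacy is not among the stopping grounds listed for the DSMB. Such a stop would itself depart from the 384-death plan after regulatory discussion, and SAP 1 allows the plan to be revised for regulatory requests before database lock.

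The point may also be spent. SAP version 4 is dated March 2017, the planned study period ended in December 2015, and that version still plans the final analysis at about 384 deaths. This suggests, without proving, that the 192-death look had passed.

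Nor is it a fault that 7.4 writes 0.05 for OS where 7.3 gives 0.003051 and 0.049002. The first paragraph of 7.4 names the spending function, so 0.05 there is the overall level.

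**Conclusion.** No change follows. Followed as written, the plan tests PFS and ORR once, at about 384 deaths, and only if OS has succeeded. The hierarchy then holds at 5% for any correlation and any OS effect. The gap is an unwritten policy for a discretionary stop, which the sponsor and regulator would have to settle if it arose.

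If that stop occurred and PFS were tested once at 0.05, the two-sided-equivalent error would be about 5.0% to 6.0% at OS hazard ratio 0.75. Since only superiority of AEZS-108 is claimed, the false-favourable rate would be half of that, about 2.5% to 3.0% against 2.5%. These sizes rest on correlations of 0.3 to 0.7 and PFS medians of 3 to 7 months, none of which are in the documents. Higher correlations can take the error to about 6.9%, and low correlation with a smaller OS effect takes it below 5%. A sentence in 7.4 stating a single final test, with descriptive reporting after an early stop, would only record the existing plan and alter no planned result.
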